[figure not shown]
Study Title: Feasibility Study of Compassion Meditation Intervention for Older Veterans in Primary Care with Anxiety or Mood Disorders

NCT #: NCT03964246

Date of Document: 09/21/2020

4) What is the estimated duration of the entire study? (From IRB approval to IRB closure)					
36 months					

Section 5 - Lay Language Summary

5) Provide a summary or synopsis of the proposed study using non-technical language (not more than 1 paragraph)

Many older Veterans in VA primary care clinics experience anxiety and depressive symptoms, but only a minority of these Veterans seek care through VA mental health services. Research suggests that some older Veterans with psychological distress under-utilize mental health services due to perceived stigma of treatments focused on mental health symptoms. However, prior research with civilians, including one study of Veterans with PTSD, suggests a strengths-focused intervention that provides group training in compassion meditation may be effective in reducing negative emotions and increasing positive emotions and well-being. The proposed project is designed to examine the feasibility of this approach with Veterans ages > 55 years with anxiety or depression. Twenty to 30 participants will be enrolled in a 10-week CM training group (with 8-10 participants in each group). The groups will be conducted with a manualized CM intervention, although part of the goal of the feasibility study is to identify and adapt the intervention to the needs of this specific population. As part of establishing feasibility for a subsequent large-scale study, 10 additional participants will be enrolled in a 10-session manualized psychoeducational group focused on topics in healthy aging. The latter group will be conducted to examine the feasibility and appropriateness of employing this as a control condition in a larger follow-up study. The information from the study will guide and support development of a larger-size, more definitive study, planned as the follow-up after this project. If successful, this line of research could open the door to a novel and effective treatment that widens acceptance by older Veterans with psychological distress.

Section 6 - Specific Aims

6) Provide a statement of specific aims and hypotheses that serve as the basis for this protocol. Emphasize those aspects that justify the use of human subjects.

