CM intervention: Through the experience and feedback from the three successful CM groups we will adapt the CBCT-Vet([name] et al., 2017) intervention for use in older adults with anxiety or depressive symptoms. This adaptation will be conducted with input from [name] and [name] (developers of CBCT® and consultants for the proposed project), and the experience and expertise of the study team. Expected adaptations include changing the focus of examples from PTSD to anxiety and depression, as well as adjustments for appropriate use with older Veterans. The CBCT-Vet includes 10 90-minute sessions that will be led by [name], a VA Staff Psychologist and Co-Investigator on the proposed project, who is certified in CBCT® with significant experience in administering CBCT-Vet. Sessions 1 - 4 assist participants in basic mindfulness breathing practices; sessions 4 - 8 focus on personal analysis of factors underlying difficulties with compassion for self or others; the final two sessions (9 and 10) review content and assist with relapse prevention. Session by session topics are: (1) Introduction and learning breathing meditation, (2) Focused attention, (3) Creating space, (4) Mindful awareness, (5) Re-engaging with heroic spirit, (6) Seeing ourselves in others, (7) Appreciation and gratitude, (8) Empathy and engaged compassion, (9) "Putting it all together," and (10) "Putting it all together 2."

Our target is to have 5-8 participants completing each 10-week intervention, thus we will enroll up to 10 per group to account for possible attrition. Two or three of the CBCT-Vet groups (depending on the degree of modification needed based on the initial group) will be conducted sequentially, such that information in the first group can be used to adapt the manualized intervention for the next group.

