Descriptive statistics will be used to summarize the variables as well as to detect outliers and data entry errors. When applicable, normality of the distribution will be examined for outcome variables and residuals of regression model with a normal probability plot. The present project is intended as a feasibility study that will inform, support, and guide development of a subsequent larger-scale VA Merit Award project. Therefore, the primary analysis will be descriptive rather than hypothesis testing. Since the interventions are delivered by group (8-10 participants per group), it is possible that measured or unmeasured characteristics of the participants in a given group or their interactions may affect psychological response to the intervention, attendance, and study outcomes. The analysis plan described below is based on no cluster effect of class. But we will assess the impact of clustering effects by fitting a random effects model for each outcome, and, if necessary, a random class effect will be included in the model to account for the correlations between the individuals in the same class. The intraclass correlation coefficient (ICC) will also be estimated to understand the correlation within class and provide advice for sample size adjustment in future studies.

Will older Veterans with psychological distress [anxiety and/or depression] enroll in and complete the proposed CM intervention? What is the completion rate? Do participants adhere to the treatment (complete practice at home)? We will assess the following outcome measures for enrollment, completion, and adherence to treatment:

- 1) $\underline{\it Enrollment\ rate}$ defined as the proportion of consented subjects among all screened and eligible patients;
- 2) Initiation rate defined as the proportion of subjects who initiate the intervention among all consented subjects;
- 3) $\underline{Completion\ rate}$ defined as the proportion of subjects who complete 6 or more sessions (out of a total of 10 sessions) of intervention among those who start the intervention;
- 4) Practice time at home defined as average minutes that subjects practice at home each week. The mean (and SD) or percentage will be calculated and the 95% confidence intervals will be estimated for all outcomes.

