The associations between patient characteristics and other clinically important baseline variables with the enrollment, completion and adherence will be assessed using univariate tests (Wilcoxon rank sum test, Kruskal-Wallis test, Fisher's exact test, or Spearman correlation coefficient).

Does CM show promise for improving well-being, symptom severity, and/or positive psychological factors relevant to successful aging? We will evaluate the improvement in depression and anxiety (BSI), social connection (SCS-R), satisfaction with life (SWLS) and positive emotions (mDES) from baseline to post-intervention using a linear random effect model and time will be included as a main effect in the model. The random effects model is suitable for examining changes in outcomes in longitudinal studies. It will include all available data, minimizing the effects of missing data on the analyses.

We will also examine the mean (and SD) change scores for each inflammatory biomarker (hs-CRP, IL-6, and TNF-), as well as the association of these changes with practice time.

Sample size assessment:

The sample size was determined based on practical consideration. Since this is a feasibility study, the goal is to examine the effect size such that it can guide future studies. We plan to enroll a total of approximately 24 to 30 participants for the CM groups (3 groups, 8-10 per group) as well as 10 participants for the healthy aging group. Sample size analyses were focused on the CM group, and performed using statistical package R.

A two-sided type I error of 0.05 was assumed.

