The sample size justification was conducted for assessing the enrollment and completion rates (primary outcomes). We assessed the precision of estimates based on projected sample size. From previous investigations, the estimated enrollment and completion rates are between 0.57 and 0.82. Therefore, we considered a range of rate from 0.60 to 0.90 and estimated the margin of error (half of the width) for the 95% confidence interval of enrollment and completion rates. The margin of error of a 95% confidence interval for a proportion is 1.96*p*(1-p)/(Square-root of n) where n is the estimated sample and p is the estimated rate. If an estimated intervention initiation rate is 0.80, a sample size of 30, 27 and 24 will produce a two-sided 95% confidence interval with a margin of error of 0.058, 0.071 and 0.064, respectively. For an estimated completion rate of 0.60, a sample size of 30, 27 and 24 will produce a two-sided 95% confidence interval with a margin of error of 0.086, 0.091 and 0.096, respectively.

We assessed the power for detecting a significant change in psychological outcomes. With a sample size of 24, 27 and 30, we will have 80% power to detect an effect size of 0.53, 0.56 and 0.60 for the change in outcomes from baseline to post-intervention. These effect sizes are achievable based on previous studies, where we observed an effect size of 0.5 for PHQ-9 (mean = 2.3, SD = 4.6), 0.65 for SCS-R (mean = 6.4, SD = 9.9), 1.4 for SWLS (mean = 9.0, SD = 6.6), 0.53 for mDES positive emotion (mean = 4.8, SD = 9.1), and 5.35 for mDES negative emotions (mean = 7.5, SD = 1.4).

Women and ethnic minorities: Women and ethnic minorities will be included in proportion to their representation of Veterans in the VASDHS and PCMHI program. This proportional sampling plan fosters both feasibility of the study and overall generalizability of findings. We recognize that the issues of anxiety and depression among women Veterans is exceptionally important, but warrants separate studies designed and focused specifically to address the issues of most salience to women Veterans.

Children: No children will be included as the scientific focus of this project is on older Veterans

Temporary COVID-19 Updates*

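### The power sentence pairs sample sizes with the wrong effect sizes, and its n assumes three fully enrolled classes with no loss, which the design does not guarantee

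*Combined protocol and SAP*

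**What the plan says.** All places are in the combined protocol and SAP.

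- **Power (Section 9, Sample size assessment).** "With a sample size of 24, 27 and 30, we will have 80% power to detect an effect size of 0.53, 0.56 and 0.60" for change from baseline to post-intervention, at a two-sided type I error of 0.05. The text then calls these effects achievable in the light of earlier studies.
- **Enrolment behind it (same subsection).** About "24 to 30 participants for the CM groups (3 groups, 8-10 per group").
- **Number of classes (Section 9, CM intervention).** "Two or three of the CBCT-Vet groups (depending on the degree of modification needed based on the initial group") are to be run one after another.
- **Lower end of enrolment (Section 5, Lay Language Summary).** "Twenty to 30 participants will be enrolled in a 10-week CM training group".
- **Attrition (Section 9, CM intervention).** "Our target is to have 5-8 participants completing each 10-week intervention", "thus we will enroll up to 10 per group to account for possible attrition". The Sample size assessment also cites earlier enrolment and completion rates of 0.57 to 0.82, but uses them only for the precision of the rates.
- **Completion (Section 9, Analytic plan).** A completer is someone "who complete 6 or more sessions (out of a total of 10 sessions").
- **Missing data (Section 9, Analytic plan).** Of the random effects model: "It will include all available data, minimizing the effects of missing data on the analyses".

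**The concern.** Two things look wrong. First, at fixed power and alpha a larger sample detects a smaller effect, but the sentence gives the smallest effect to the smallest sample and the largest effect to the largest.

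Second, the n in the sentence is the number enrolled, whereas power for within-person change depends on how many people have both a baseline and a post-intervention value. The three sample sizes match the three-class enrolment range exactly, so no loss is built in, and other parts of the plan permit fewer classes or a lower enrolment floor.

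The study is meant to supply effect sizes for a later, larger trial. A reader who relies on this sentence to judge what the pilot can show would take a wrong n-to-effect pairing, and an n the design may not deliver.

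**Working it through.** **Inputs.** Alpha 0.05 two-sided, 80% power, n = 24, 27, 30 and effects 0.53, 0.56, 0.60 (Sample size assessment). The comparison is within-person change in the CM participants. The documents do not name the test; a one-sample t-test on change scores is assumed.

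**Formula.** With d = mean change / SD of change and n complete pairs, the noncentrality is d × √n on n − 1 degrees of freedom. Power is the probability that a noncentral t with that noncentrality falls outside ± t(0.975, n − 1).

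**Step 1: the plan's own figures.**

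| Pairing | n | d | d × √n | Power |
|---|---|---|---|---|
| As printed | 24 | 0.53 | 2.60 | 70.1% |
| As printed | 27 | 0.56 | 2.91 | 80.0% |
| As printed | 30 | 0.60 | 3.29 | 88.8% |
| Reversed | 24 | 0.60 | 2.94 | 80.4% |
| Reversed | 27 | 0.56 | 2.91 | 80.0% |
| Reversed | 30 | 0.53 | 2.90 | 80.1% |

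The printed pairing also fails with a one-sided t-test (80.9%, 88.3%, 94.1%) and with a normal approximation (73.8%, 82.9%, 90.8%). With the order reversed, all three pairs reproduce. So the values are right, their order is wrong, and n is the number of complete pairs.

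**Step 2: where n comes from.** 3 × 8 = 24 and 3 × 10 = 30. These are the enrolment limits for three classes, so the calculation treats everyone enrolled as a complete pair.

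**Step 3: smaller designs the documents permit.** Two classes of 10 give 2 × 10 = 20, which is also the lay summary's floor. Two classes of 8 would give 2 × 8 = 16; that number is derived, not stated, and lies below the floor.

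| Complete pairs | Detectable d at 80% power | Power for d = 0.60 |
|---|---|---|
| 30 | 0.53 | 89% |
| 24 | 0.60 | 80% |
| 20 | 0.66 | 72% |
| 16 | 0.75 | 61% |
| 15 | 0.78 | 58% |

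Fifteen is three classes at the lower completer target (3 × 5). It is shown only to extend the range.

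**Step 4: room for loss with three classes.** For d = 0.60, 24 pairs are needed (23 give 78.5%). The losses that can be absorbed are therefore 24 − 24 = 0 with 24 enrolled, 27 − 24 = 3 with 27, and 30 − 24 = 6 with 30. Six of 30 is 20%.

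**The case against.** The strongest reply is that little depends on the sentence. The sample size was set on practical grounds, the primary analysis is descriptive, efficacy is not to be tested inferentially, and the primary outcomes are the enrolment and completion rates. That stands, and it limits the severity. It does not make a stated 80% correct when it is 70% or 89%.

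Four stronger readings are tempting, and the documents do not support them.

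- **That 80% power needs post data from everyone in the 24-30 range.** This holds only at 24 enrolled, or if each n must keep its own paired effect. With 27 or 30 enrolled, 3 or 6 can be lost and power for 0.60 is kept.
- **That the plan ignores attrition.** It over-enrols for attrition and cites earlier rates. The narrower statement is that neither enters the power n and no rate of post-assessment retention is given.
- **That the completer target is a worst case for post data.** Completion is attendance at a set number of sessions, not attendance at the final assessment. Non-completers may be assessed, and the plan mails questionnaires to participants who withdrew during the COVID-19 hold. Completers may miss the final visit, and completion may fall below target. The target is therefore neither a forecast nor a bound.
- **That the plan sets enrolment at 16.** No section says so, and the lay summary's minimum is 20.

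The model's use of all available data helps only in part. For measures taken only at baseline and post-intervention, someone with a baseline value alone adds little about change. The mDES is collected weekly, so early leavers do contribute there. Elsewhere the CM intervention text speaks of three groups, but it goes on to allow two or three, so the inconsistency remains.

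**Conclusion.** The point holds, and it is minor. The power sentence is wrong as printed: two of its three pairings miss 80%, one by about 10 points below and one by about 9 above. Once the order is corrected, the figures apply only if three classes are run and the stated number of complete pairs is obtained. At the lay summary's floor of 20, with no loss at all, power for 0.60 is 72% and the detectable effect is 0.66. If two classes of 8 were run, 16 pairs would give 61% and 0.75.

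The conclusion assumes a paired t-test, which the plan's own values support once reordered, and no class effect, as the Analytic plan assumes for its base case. The number with post data is not given in the documents, so it is shown as a range. No decision rule depends on the figure.

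**What to change.** 1. In the Sample size assessment, pair 24 with 0.60, 27 with 0.56 and 30 with 0.53.
2. Reconcile the number of CM classes and the CM enrolment across the Lay Language Summary, the CM intervention text and the Sample size assessment. If two classes remain possible, add a row for them: 20 pairs 0.66, and 16 pairs 0.75 if classes of 8 are allowed.
3. State the detectable effect by number of complete pairs under an explicit assumed range of post-assessment retention, for example 30: 0.53, 24: 0.60, 20: 0.66, 16: 0.75, 15: 0.78. Do not label the completer target as a worst case.

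The cost is text only, with no extra participants and no change to the analysis. The downside is that the stated power becomes less favourable. If the inconsistency is instead settled by committing to three classes, the option of stopping at two is given up.

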Psychoeducational healthy aging group: As part of this project, we will develop and test a 10-week psychoeducational group focused on topics in healthy aging to examine its feasibility as a control condition for a subsequent VA Merit-supported randomized controlled trial. [name], in addition to his VA position and roles, is an active member of the Center for Healthy Aging at UC San Diego. The Center for Healthy Aging has multiple resources for community education regarding healthy aging, including a library of videotaped community-focused talks, such as increasing happiness, mental resilience and health, nutrition, and physical activity. We will incorporate these videos as part of 90-minute sessions wherein the key information from talks is shown to participants, with a follow-up discussion and review period led by the group facilitator. In the context of the present feasibility study, we anticipate modifying and refining the content and format of the group in response to participant feedback.

Process and outcome measures: As a feasibility study, we will not be testing hypotheses regarding the efficacy of CBCT-Vet in reducing psychological distress with inferential statistics. However, in order to support our planned subsequent VA Merit application, we will be examining descriptive statistics of observed patterns and estimated effect sizes of change on key measures described below.

Baseline and post-intervention: Each participant will meet individually with a trained Research Assistant (RA; To Be Named (TBN)) for two 90-minute assessment sessions (baseline and post-intervention). The final assessment will be scheduled within 2-weeks of the participant's final intervention group session. Measures will include:

Psychological distress: Brief Symptom Inventory-18 (BSI; depression, anxiety, and somatization) (Boulet & Boss, 1991).

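### The plan disowns inferential testing of efficacy but claims 80% power for a significant pre-post change; a precision statement should replace the power sentence

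*Combined protocol and SAP*

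**What the plan says.** Two places in Section 9 commit the study to description. Process and outcome measures states that "we will not be testing hypotheses regarding the efficacy of CBCT-Vet in reducing psychological distress with inferential statistics" and offers in its place descriptive statistics and "estimated effect sizes of change on key measures described below". The Analytic plan adds that "the primary analysis will be descriptive rather than hypothesis testing".

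The Sample size assessment, also in Section 9, points the other way. It says "A two-sided type I error of 0.05 was assumed". After the precision work for enrollment and completion, which it names as the primary outcomes, it continues "We assessed the power for detecting a significant change in psychological outcomes" and then "With a sample size of 24, 27 and 30, we will have 80% power to detect an effect size of 0.53, 0.56 and 0.60". It calls those effects achievable on the basis of earlier studies. The sample is "approximately 24 to 30 participants for the CM groups (3 groups, 8-10 per group").

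The efficacy analysis is in the Analytic plan: "We will evaluate the improvement in depression and anxiety (BSI), social connection (SCS-R), satisfaction with life (SWLS) and positive emotions (mDES"), by a linear random effect model with time as a main effect. It answers the question whether CM shows promise in any of three broad domains. The plan does not define promise, name a lead efficacy outcome, adjust for multiplicity or give a p-value rule. The Analytic plan also lists univariate tests of baseline variables against enrollment, completion and adherence.

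**The concern.** A power figure for a significant change presupposes that change will be tested. An analyst who follows Process and outcome measures would report effect sizes. One who follows the Sample size assessment would report p-values against 0.05. Both could claim to have followed the plan, and the reports would read differently.

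What is at stake is the message carried into the planned Merit application. If p-values are reported on several scales without adjustment or a lead outcome, one small p-value could be taken as evidence of efficacy from a single-arm pre-post comparison that the plan says is not an efficacy test. The primary feasibility outcomes are unaffected.

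**Working it through.** **1. What kind of figure the power claim is.** Inputs from the Sample size assessment: two-sided alpha 0.05, power 80%, n = 24, 27 and 30, effect sizes 0.53, 0.56 and 0.60 in SDs of change. Method: paired (one-sample) t-test, noncentral t with n − 1 degrees of freedom and noncentrality d√n.

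| n | d detectable at 80% power | d printed beside this n | power at printed d |
|---|---|---|---|
| 24 | 0.597 | 0.53 | 70.1% |
| 27 | 0.560 | 0.56 | 80.0% |
| 30 | 0.529 | 0.60 | 88.8% |

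The printed effect sizes are recovered to two decimals, but in reverse order to the sample sizes. Neither alternative tried gives the set: a one-sided 0.05 test gives 0.52, 0.49 and 0.46, and the normal approximation gives 0.57, 0.54 and 0.51. The figures therefore come from a two-sided 0.05 significance test of change, the type of inference that Process and outcome measures says will not be used for efficacy.

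**2. What unadjusted testing could do.** Count five scores: BSI depression, BSI anxiety, SCS-R, SWLS and mDES positive emotion. Suppose each change is tested two-sided at 0.05 and there is no true change. Only a significant improvement could be read as promise, so each score contributes 0.025. If the scores are independent:

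1 − (1 − 0.025)^5 = 1 − 0.975^5 = 1 − 0.881 = 0.119, about 12%.

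The documents give no correlations between change scores, so a range is assumed. Simulation of five equicorrelated changes (20,000 replicates) gives the chance of at least one favourable result:

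| assumed correlation | n = 24 | n = 30 |
|---|---|---|
| 0 | 11.4% | 11.8% |
| 0.3 | 10.4% | 10.7% |
| 0.5 | 9.1% | 9.3% |
| 0.7 | 7.9% | 7.5% |

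The benchmark for a single score is 2.5%.

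**3. What the design gives as an estimate.** The 95% CI half-width for a mean change, in SDs of change, is t(0.975, n − 1)/√n:

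- n = 24: 2.069/4.899 = 0.42
- n = 27: 2.056/5.196 = 0.40
- n = 30: 2.045/5.477 = 0.37

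These assume that everyone has both assessments. The CM intervention paragraph targets 5 to 8 completers per group, so three groups give 3 × 5 = 15 to 3 × 8 = 24. At n = 15 the half-width is 2.145/3.873 = 0.55. Completers stand in here for participants with both assessments. Any class effect, which the Analytic plan says it will examine, would widen these intervals.

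**The case against.** The strongest reply is that this is a wording slip in a feasibility study. The primary outcomes are rates, the primary analysis is descriptive, a definitive trial is to follow, and multiplicity control for secondary estimates is not obligatory. That stands, and it is why no adjustment is asked for.

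The literal conflict can also be narrowed. The disclaimer concerns psychological distress, for which the BSI is the listed measure; SCS-R, SWLS and mDES stand under other headings. That is fair, but the power sentence covers psychological outcomes without exception, and the earlier effects cited for it begin with the PHQ-9, a depressive-symptom scale. The conflict does not go away.

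Several stronger readings are tempting, and the documents do not support them:

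- A reader might infer that one significant scale suffices to declare promise, because the question joins its domains by and/or. That phrase joins three domains in a research question. No passage makes a p-value the criterion.
- A reader might take the time effect in the random effect model as a hypothesis test. It can equally serve to estimate mean change, and the plan justifies the model by its use of all available data.
- A reader might quote a two-sided familywise figure: about 22.6% for five independent scores, or about 21% to 15% at correlations 0.3 to 0.7. That counts significant worsening as promise and roughly doubles the relevant risk.
- A reader might say that the univariate tests also breach the disclaimer. They concern enrollment, completion and adherence, not efficacy. Crossing 24 possible baseline variables with completion and practice time gives 48 tests, 48 × 0.05 = 2.4 expected false positives and 1 − 0.95^48 = 91% for at least one. That is a ceiling: the plan limits the variables to patient characteristics and others of clinical importance, biomarker collection is suspended during the COVID-19 hold, and overlapping scales are not independent.

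Finally, the Analytic plan does promise 95% confidence intervals for all outcomes. That sentence closes the list of feasibility measures, so whether it reaches the efficacy changes is arguable.

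**Conclusion.** The contradiction is real but narrow. Process and outcome measures and the Analytic plan commit to description; the Sample size assessment claims power for a significance test of change, and its figures are reproduced only as such a test. The consequence is a possibility that the plan leaves open, not a rule that it sets. If unadjusted p-values on five scores were read as efficacy evidence, the chance of at least one favourable false positive is about 12% under independence and about 10.7% to 7.5% at correlations 0.3 to 0.7, against 2.5% for a single score. The result rests on counting the two BSI scores separately and on the assumed correlations. The feasibility objectives are untouched.

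**What to change.** In the Sample size assessment, remove the sentences claiming power for a significant change and give the half-widths from step 3: about 0.42, 0.40 and 0.37 SD of change at n = 24, 27 and 30 with complete data, and about 0.55 SD if only 15 complete, all before class clustering. This also disposes of the misordered effect sizes.

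Keep the 0.05 but say that it sets the level of the 95% confidence intervals; it precedes the interval work for the primary rates and should not simply be deleted. In the Analytic plan, state that each efficacy change (BSI, SCS-R, SWLS, mDES) is reported as an estimate with its 95% CI and that no p-value decides promise. Label the baseline-association tests exploratory.

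The cost is a few sentences. The sponsor gives up a power statement that its own design paragraph disowns; no data collection or sample size changes.

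### The completion-rate interval allows for class only on an unstated trigger, and its planned margin has no design effect, so both are too narrow if attendance clusters by class

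*Combined protocol and SAP*

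**What the plan says.** All of this is in Section 9.

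- **Reason to expect clustering.** The Analytic plan notes that the treatment is given in groups, and that the make-up of a group or the interactions in it "may affect psychological response to the intervention, attendance, and study outcomes".
- **Default.** "The analysis plan described below is based on no cluster effect of class".
- **Safeguard.** Every outcome is to get a random effects model, as a way to gauge how much clustering matters. Keeping the class term is conditional: "if necessary, a random class effect will be included in the model to account for the correlations between the individuals in the same class". An ICC is to be estimated as well, to describe similarity within classes and with a view to sizing later studies. The plan gives no test, level, information criterion or ICC cut-off for deciding when the class effect is needed.
- **Outcome.** Completion is the share of participants who "complete 6 or more sessions (out of a total of 10 sessions) of intervention among those who start the intervention". For the feasibility measures, "the 95% confidence intervals will be estimated for all outcomes"; no interval method is named.
- **Planned precision.** Sample size assessment names enrollment and completion as the primary outcomes. For a completion rate of 0.60 at n = 30, 27 and 24 it gives an interval "with a margin of error of 0.086, 0.091 and 0.096".
- **Number of classes.** Sample size assessment plans three compassion meditation classes of 8–10. The CM intervention paragraph allows two or three, run in sequence, with the manual adapted between them.

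**The concern.** The plan names a threat to a primary outcome and then computes that outcome's precision as if the threat were absent. Completion is a count of sessions attended, so anything shared by a class (its facilitation, its version of the manual, its mode of delivery) can move its members together. The documents give concrete examples. The manual changes between classes, and the COVID-19 updates describe a first cohort moved to virtual sessions partway through, with three withdrawals for lack of technology.

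The study is descriptive, so the completion rate and its 95% interval are a main product and will inform the larger trial. If attendance clusters and the interval is not adjusted, it covers less often than stated. A decision to adjust that is made after seeing the data, on no stated rule and with two or three classes, is weak protection.

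**Working it through.** **Inputs.** From the plan: three classes, m = 8, 9 or 10 per class (n = 24, 27, 30), completion rate p = 0.60, two-sided 95%. Assumed here: ICC of 0.02, 0.05 and 0.10, equal class sizes, all enrolled participants start, and class completion rates that follow a beta distribution (beta-binomial counts).

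**1. The plan's own margins.** The printed formula is 1.96·p·(1−p)/√n. At p = 0.60, p(1−p) = 0.24:
- n = 30: 1.96 × 0.24/√30 = 0.0859
- n = 27: 1.96 × 0.24/√27 = 0.0905
- n = 24: 1.96 × 0.24/√24 = 0.0960

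These match the printed 0.086, 0.091 and 0.096. The formula contains no design effect. It also lacks the square root over p(1−p). The standard margin is 1.96·√(p(1−p)/n), which is larger by 1/√0.24 = 2.04.

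**2. Standard margins with a design effect.** Margin = 1.96·√(0.24/n × DEFF), with DEFF = 1 + (m−1)·ICC. For example, n = 24, m = 8, ICC 0.05: DEFF = 1.35 and the margin is 1.96·√(0.01 × 1.35) = 0.228.

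| ICC | n = 30 | n = 27 | n = 24 | widening, √DEFF − 1 |
|---|---|---|---|---|
| 0 | 0.175 | 0.185 | 0.196 | – |
| 0.02 | 0.190 | 0.199 | 0.209 | 7–9% |
| 0.05 | 0.211 | 0.219 | 0.228 | 16–20% |
| 0.10 | 0.242 | 0.248 | 0.256 | 30–38% |

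**3. Coverage without adjustment.** This is the probability that the interval contains 0.60, for three classes of 8 or 10. Wilson is the better gauge of clustering, because the simple Wald interval already falls to about 94% with no clustering.

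| ICC | Wilson | Wald |
|---|---|---|
| 0 | 96% | 94% |
| 0.02 | 94–95% | 91–92% |
| 0.05 | 91–93% | 87–89% |
| 0.10 | 86–89% | 81–84% |

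These come from 20,000 simulated trials per setting. Summing the beta-binomial probabilities over all class outcomes agrees to within a point. Classes of 9 come out up to about one point below the lower Wilson figures at ICC 0.02 to 0.10.

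**4. How often a check would lead to adjustment** (three classes of 8 or 10, p = 0.60). The plan states no rule, so several are shown.

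| Rule | ICC 0.05 | ICC 0.10 |
|---|---|---|
| 5% chi-square across classes | 12–13% | 21–22% |
| 5% likelihood-ratio test of class variance | about 5.5% | 10–12% |
| AIC | 7–9% | 12–17% |
| Estimated ICC above 0 | 52–53% | 62% |

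Even the most lenient rule leaves the interval unadjusted in about 47–48% of trials at ICC 0.05 and 38% at 0.10. With two classes, the chi-square check fires in 9–12% and 15–17%.

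**The case against.** The plan does not ignore clustering. It raises the issue itself, commits to a random effects model for each outcome, and will estimate the ICC. The study is descriptive, its size was set on practical grounds, and no go/no-go threshold hangs on the interval. All of that stands, and it limits the weight of the point. It does not fill the gap: the stated use of the ICC is to understand within-class correlation and to advise on later sample sizes, and nothing ties the reported completion interval to it.

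A reader might infer that the check will rarely fire and that the interval will usually be too narrow. The documents support neither. A low firing rate assumes a significance or AIC rule, and the plan states none. If adjustment followed any positive ICC estimate, it would happen in over half of trials, and Wilson coverage would be about 94–95% at ICC 0.05, though only 91–93% at 0.10. Whether the interval is too narrow depends on a true ICC that the documents do not give; at 0.02 the loss is small.

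A reader might also take every primary interval to be affected. Enrollment is measured among eligible patients before any class session, so the point does not reach it.

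Finally, the printed margins might be read as the correct no-clustering case, with clustering to blame for the gap up to 0.211 or 0.242 at n = 30. That is wrong. Most of the gap is the missing square root (0.086 against 0.175), a separate and larger fault.

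**Conclusion.** The concern holds in a limited form. The completion interval treats members of a class as independent unless an undefined trigger is met, and the planned completion margin makes no allowance for class at all. If attendance clusters, the interval is too narrow: slightly at ICC 0.02, by 16–20% in width at 0.05, and by 30–38% at 0.10, with Wilson coverage of 86–89% in the last case. With two or three classes, a significance-type check would seldom reveal this.

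The size rests on assumed ICC values, equal classes, the beta-binomial model and p = 0.60. The conclusion covers completion only. It is conditional on clustering that the plan considers possible but does not quantify.

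**What to change.** **Analytic plan.** For the completion rate, remove the data-dependent condition. Always report completion by class. Beside the simple 95% interval, give sensitivity intervals inflated by DEFF = 1 + (m−1)·ICC at stated values such as 0.02, 0.05 and 0.10, with m the mean number of starters per class. Name the interval method. Fixed ICC values avoid resting the interval on a class variance estimated with two degrees of freedom, or one if only two classes run.

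**Sample size assessment.** Do not describe 0.086, 0.091 and 0.096 as the no-clustering case. State the standard-formula margins at p = 0.60 (0.175, 0.185, 0.196 at n = 30, 27, 24) and add the clustered rows from the table above.

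**Cost.** A few sentences of SAP text and three extra intervals, with no added participants. The downside is that the stated precision looks worse: by 7–9%, 16–20% or 30–38% for clustering at the three ICC values, on top of the roughly twofold increase from correcting the formula. The two changes should be shown separately so that neither is mistaken for the other.
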